#### **6.1.2.2 Epoetin Alfa Treatment**

##### Subjects in both the Main and ESA hyporesponder parallel study randomized to epoetin alfa:

All subjects randomized to epoetin alfa will receive TIW dosing for the entire Treatment Period based on the subject's central laboratory Hb value and the approved epoetin alfa United States (US) Package Insert (PI) for adult patients with CKD on dialysis. Dose will be adjusted to achieve and maintain Hb levels within the target range of 10.0 to 11.0 g/dL, inclusive, while targeting the middle of the range and minimizing excursions outside of the target range (see [Section 8.4.4](#), Epoetin Alfa Dosing Regimen).

### **6.1.3 Safety Follow-Up Period (Weeks 20 to 24)**

For all subjects (Main and ESA hyporesponder parallel study), the 4-week Safety Follow-Up Period starting at Week 20 will be followed by a post-treatment safety assessment conducted at the beginning of Week 24.

## 6.2 Rationale for Study Design

The Main Study and the ESA hyporesponder parallel study will evaluate different starting doses of vadadustat based on pre-baseline ESA doses. Numerous studies have demonstrated that hemodialysis patients requiring higher ESA doses to treat their anemia have a higher burden of comorbidities, a more inflammatory state, and a greater risk of adverse outcomes ([Besarb 1998](#); [Parfrey 2005](#); [Unger 2010](#)). As described above ([Section 4.2](#), Summary of Clinical Experience) in a Phase 2 hemodialysis study (CI-0011), a post-hoc analysis suggested higher pre-baseline ESA doses were associated with lower observed mean Hb levels. Subjects on higher pre-baseline ESA doses may benefit from a higher starting dose of vadadustat after initial conversion from ESAs.

Three levels of pre-baseline ESA dose will be evaluated. In the Main Study subjects will be randomized to one of two cohorts based on pre-baseline ESA dose ( $\leq 90$  U/kg/week and  $>90$  to  $<300$  U/kg/week). The ESA threshold of 90 U/kg/week was based on the median ESA doses reported in the US Renal Data System and US Dialysis Outcomes and Practice Patterns Study, which ranged from approximately 90 to 110 U/kg/week.

The ESA hyporesponder parallel study will evaluate subjects with Hb levels below the target range despite receiving  $\geq 300$  U/kg/week of epoetin alfa. This ESA threshold was based on the definition of resistance to ESAs proposed in the ERA-EDTA 2004 guidelines ([Locatelli 2004](#)).

The Main study and the ESA hyporesponder parallel study incorporate an approach to vadadustat dose adjustment designed to maximize the probability that Hb can be maintained within the target range of 10.0 to 11.0 g/dL, inclusive (see [Section 8.4.5](#), Vadadustat Dosing Regimen and Guidelines for Dose Adjustment). The approach to vadadustat dose adjustment in this Phase 2 study includes several modifications as compared to the vadadustat dosing algorithms used in previously completed Phase 2 studies and the dosing algorithm used in the ongoing Phase 3 studies.

During this study, dose increases for vadadustat will be allowed at 4-week intervals, with the exception of the initial 2 weeks of treatment, in the daily and TIW dosing periods of the study. Dose increases will be permitted in the initial 2 weeks of treatment, in the daily and TIW dosing periods, in subjects with a Hb decline  $\geq 0.5$  g/dL from baseline and Week 12, respectively. This approach is commonly used in clinical practice to treat patients with declining or low Hb values ([Pfeffer 2009a](#); [Singh 2006](#)). Risk of abrupt or excessive increases in Hb is minimized due to the underlying Hb trajectory and is further mitigated by close Hb monitoring.

In the present study, the safety and efficacy of a vadadustat TIW dosing regimen is being evaluated as a potential alternative treatment regimen to a once daily dosing regimen in hemodialysis subjects. Specifically, this study will evaluate conversion from once daily dosing to TIW dosing. As described above ([Section 4.2](#), Summary of Clinical Experience), the 16-week Phase 2 hemodialysis study evaluated hemodialysis subjects switching from ESA to vadadustat 450 mg TIW for an 8-week fixed-dose period followed by 8 weeks of dose adjustment according to Hb response. The primary efficacy analysis in CI-0011 using observed data showed stable mean Hb levels in this group. Six of 31 (19%) subjects withdrew due to worsening anemia, and a sensitivity analysis imputing missing Hb values using LOCF demonstrated a decline in mean Hb levels. To maximize the probability that subjects treated with vadadustat TIW will maintain Hb levels within the target range, this study will: examine subjects successfully treated with

daily dosing converting to TIW dosing; allow for earlier dose increase after 2 weeks of initial treatment; and permit dose increases up to 900 mg TIW.

### 6.3 Dose Justification

In this study, vadadustat starting daily doses will be determined by pre-baseline ESA dose ([Section 8.4.5](#), Vadadustat Dosing Regimen and Guidelines for Dose Adjustment). In the Main study starting doses of vadadustat will be 300 mg and 450 mg daily in subjects converting from epoetin alfa doses  $\leq$ 90 U/kg/week and 300 mg, 450 mg, and 600 mg daily in subjects converting from epoetin alfa doses  $>$ 90 to  $<$ 300 U/kg/week. For the ESA hyporesponder parallel study, the starting doses will be 600 mg daily. As described above ([Section 4.2](#), Summary of Clinical Experience), the maximum vadadustat starting dose evaluated in completed Phase 2 NDD-CKD studies was 630 mg or 600 mg daily, in Study AKB-6548-CI-0005 (CI-0005) and Study AKB-6548-CI-0021 (CI-0021) respectively, and in completed Phase 2 DD-CKD studies was 450 mg or 600 mg in Study AKB-6548-CI-0011 (CI-0011) and Study AKB-6548-CI-0022 (CI-0022), respectively.

Based on the dosing algorithm, vadadustat will be titrated to achieve and maintain Hb levels within the target range of 10.0 to 11.0 g/dL, inclusive. The dose range for titration is 150 mg to 900 mg daily or TIW. Doses of 150 mg to 630 mg daily have been evaluated in studies evaluating subjects with NDD-CKD and DD-CKD. The maximum vadadustat dose evaluated in healthy volunteers was 1200 mg in a single dose study (CI-0001 and CI-0010) and 900 mg daily in a 10-day multiple dose study (CI-0002), as described in [Section 4.2](#), Summary of Clinical Experience.

The rationale to evaluate higher maximum doses for titration is that to date, dose-ranging clinical studies have not identified a vadadustat dose at which a plateau in exposure or effect has been observed. In Phase 1 studies in healthy volunteers, dose-proportional increases in AUC and  $C_{max}$  and dose-related increases in serum EPO were observed up to the maximum doses studied, single doses of 1200 mg and multiple doses of 900 mg daily for 10 days (CI-0001, CI-0002). In Phase 2 studies in anemic NDD-CKD and DD-CKD subjects, dose-dependent increases in Hb were observed up to the maximum dose studied of 600 mg or 630 mg daily (CI-0005, CI-0021, CI-0022). It is anticipated that daily doses of vadadustat at 750 mg or 900 mg would yield an incremental erythropoietic effect greater than 600 mg for the treatment of renal anemia.

This study design mitigates the risk of vadadustat doses of 750 mg or 900 mg. Intensive Hb monitoring, a strict dose adjustment algorithm, and phlebotomy will be implemented to mitigate the potential risk of a rapid Hb rise, as follows:

- Hb measurements are scheduled at least every 2 weeks to Week 20
- The dose adjustment algorithm will target a narrow Hb range, 10.0 to 11.0 g/dL, inclusive
- The protocol specifies that phlebotomy may be considered in the setting of high Hb levels ( $>$ 14.0 g/dL) or a high Hb rate of rise, based on the Investigator's judgment

Importantly, the Phase 2 studies demonstrated that cessation of treatment resulted in prompt reduction in mean Hb to baseline values.

## 7 SELECTION AND WITHDRAWAL OF SUBJECTS

### 7.1 General Criteria

To be eligible for this study, a subject or their legally acceptable representative must provide valid informed consent and the subject must meet all eligibility criteria. No study procedures (including Screening tests) may be performed until after the informed consent has been legally signed.

### 7.2 Inclusion Criteria

Subjects must meet the following inclusion criteria:

1.  $\geq 18$  years of age
2. Receiving chronic, outpatient in-center hemodialysis (TIW) for ESRD for at least 12 weeks prior to Screening
3. Maintained on IV epoetin alfa therapy for 8 weeks prior to and including Screening through SV2
4. Eligibility in the Main study and ESA hyporesponder parallel study is based on the following mean weekly epoetin alfa doses:
  - Main study: Mean weekly epoetin alfa dose  $< 300$  U/kg/week for 8 weeks prior to SV2
  - ESA hyporesponder parallel study: Mean weekly epoetin alfa dose  $\geq 300$  U/kg/week for 8 weeks prior to SV2
5. Two Hb values measured at least 4 days apart by the central laboratory during Screening as indicated below
  - Main study: 2 Hb values between 8.5 and 11.0 g/dL, inclusive
  - ESA hyporesponder parallel study: 2 Hb values between 8.0 and 10.0 g/dL, inclusive
6. Serum ferritin  $\geq 100$  ng/mL and transferrin saturation (TSAT)  $\geq 20\%$  during Screening
7. Folate and vitamin B12 measurements  $\geq$  lower limit of normal during Screening
8. Hemodialysis adequacy as indicated by single-pool Kt/Vurea  $\geq 1.2$  using the most recent historical measurement within 8 weeks prior to or during Screening
9. Understands the procedures and requirements of the study and provides written informed consent and authorization for protected health information disclosure.

### 7.3 Exclusion Criteria

Subjects must not meet any of the following exclusion criteria:

1. Anemia due to a cause other than CKD (e.g., sickle cell disease, myelodysplastic syndromes, bone marrow fibrosis, hematologic malignancy, myeloma, hemolytic anemia, thalassemia, or pure red cell aplasia)
2. Active bleeding or recent blood loss within 8 weeks prior to randomization
3. RBC transfusion within 8 weeks prior to randomization
4. Anticipated to discontinue hemodialysis during the study
5. Judged by the Investigator that the subject is likely to need rescue therapy (ESA administration or RBC transfusion) immediately after enrollment in the study
6. History of chronic liver disease (e.g., chronic infectious hepatitis, chronic autoimmune liver disease, cirrhosis or fibrosis of the liver)

7. Aspartate aminotransferase (AST)/serum glutamic oxaloacetic transaminase (SGOT), alanine aminotransferase (ALT)/serum glutamic pyruvic transaminase (SGPT), or total bilirubin  $>1.5 \times$  upper limit of normal (ULN) during Screening. Subjects with a history of Gilbert's syndrome are not excluded.
8. Current uncontrolled hypertension as determined by the Investigator that would contraindicate the use of epoetin alfa
9. Acute coronary syndrome (hospitalization for unstable angina or myocardial infarction), surgical or percutaneous intervention for coronary, cerebrovascular or peripheral artery disease (aortic or lower extremity), surgical or percutaneous valvular replacement or repair, sustained ventricular tachycardia, hospitalization for heart failure (HF) or New York Heart Association Class IV HF, or stroke within 12 weeks prior to or during Screening
10. History of new or recurrent malignancy within 2 years prior to and during Screening or currently receiving treatment or suppressive therapy for cancer. Subjects with treated basal cell carcinoma of skin, curatively resected squamous cell carcinoma of skin, or cervical carcinoma in situ are not excluded.
11. History of deep vein thrombosis or pulmonary embolism within 12 weeks prior to or during Screening
12. History of hemosiderosis or hemochromatosis
13. History of prior organ transplantation (subjects with a history of failed kidney transplant or corneal transplants are not excluded)
14. Scheduled organ transplant from a living donor and subjects on the kidney transplant wait-list who are expected to receive a transplant within 6 months
15. History of a prior hematopoietic stem cell or bone marrow transplant (stem cell therapy for knee arthritis is not excluded)
16. Known hypersensitivity to vadadustat, epoetin alfa, or any of their excipients
17. Use of an investigational medication or participation in an investigational study within 30 days or 5 half-lives of the investigational medication (whichever is longer), prior to Screening (subjects may participate in another concurrent study only if that study is a non-interventional, observational investigation)
18. Previous participation in this study, or previous participation in a study with another hypoxia-inducible factor prolyl-hydroxylase inhibitor (HIF-PHI) other than vadadustat
19. For female subjects:
  - Of non-childbearing potential
    - Inability to confirm surgical sterility (e.g., hysterectomy, bilateral tubal ligation, bilateral oophorectomy) at least 1 month prior to Screening, or
    - Not considered post-menopausal (no menses for  $>1$  year with follicle stimulating hormone [FSH]  $>40$  U/L at Screening)
  - Or, if of childbearing potential,
    - Lack of confirmation of the use of acceptable forms of contraception\* for a minimum of one complete menstrual cycle prior to Screening
    - Positive serum pregnancy test at SV2
    - Unwilling to use two acceptable forms of contraception\* (at least one of which must be a barrier method) starting Baseline/Day 1, throughout the Treatment Period and for 30 days after the final study drug administration (refer to [Section 9.1.5](#), Contraception and Pregnancy Avoidance Measures)

20. Breastfeeding during Screening or throughout the Treatment Period and for 30 days after the final study drug administration.
21. Donation of ova starting at Screening, throughout the Treatment Period, and for 30 days after the final study drug administration.
22. Male subjects who have not had a vasectomy and do not agree to the following: use of an acceptable form of contraception\* (refer to [Section 9.1.5](#), Contraception and Pregnancy Avoidance Measures) during the study and for 30 days after the last dose of the study drug; to not donate semen during the study and for at least 30 days after the last dose of vadadustat.
23. Subjects with bilateral native nephrectomy.
24. Any other reason, which in the opinion of the Investigator, would make the subject not suitable for participation in the study.

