### **9.1.5 Contraception and Pregnancy Avoidance Measures**

In nonclinical animal embryo-fetal development and fertility studies, there was no evidence of teratogenicity, no skeletal or visceral malformations, and no changes in male or female reproductive and fertility indices, or in sperm parameters. In rats, decreased fetal body weight and reduced skeletal ossification were noted at the highest dose tested of 160 mg/kg/day.

Peri-postnatal development studies of vadarustat in the rat are ongoing, and there are no data on the transmission of vadarustat in breast milk or the effect of vadarustat on infants.

Although the potential risk of vadarustat on the developing fetus is limited based on studies to date, the study requires that all subjects must agree to use adequate contraception throughout the study and for 30 days after the last dose of study drug.

Adequate contraception for subjects is defined as follows:

- For females of non-childbearing potential
  - Confirmation of surgical sterility (e.g., hysterectomy, bilateral tubal ligation, bilateral oophorectomy) at least 1 month prior to Screening, or
  - Post-menopausal (no menses for >1 year with FSH >40 U/L at Screening)
- For females of childbearing potential
  - Subjects must confirm the use of acceptable forms of contraception\*, for a minimum of one complete menstrual cycle prior to Screening.

- Must have a negative serum pregnancy test at SV2.
- Starting Baseline/Day 1, subjects must use two acceptable forms of contraception\* (at least one of which must be a barrier method) throughout the Treatment Period and for 30 days after the final study drug administration
- For males subjects who have not had a vasectomy must agree to the following: use of an acceptable form of contraception\* during the study and for 30 days after the last dose of the study drug; to not donate sperm during the study and for at least 30 days after the last dose of vadadustat.

\* *Acceptable forms of contraception include:*

- *Established use of oral, injected or implanted hormonal methods of contraception.*
- *Placement of an intrauterine device or intrauterine system.*
- *Barrier methods of contraception: condom or occlusive cap (diaphragm or cervical/vault caps) with spermicidal foam/gel/film/cream/suppository.*

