## 9.2.2 Laboratory Evaluations

Samples for laboratory assays will be sent to a central laboratory for analysis. Detailed instructions for the collection, processing, and shipment of laboratory samples will be provided by the Sponsor and the central laboratory. If blood is collected on a dialysis day, blood draws

will be done prior to dialysis, if applicable. The Investigator is responsible for reviewing laboratory results for clinical significance.

For eligibility purposes, one retest for each parameter may be performed during the Screening window. Refer to [Section 7.4.1, Retesting](#) and [Section 7.4.2, Rescreening](#) for further details regarding repeating laboratory measurements during the Screening Period.

The following laboratory evaluations will be conducted during the course of the study:

- **Pregnancy Test**: A serum pregnancy test will be performed at SV2 for females of childbearing potential. Additional serum pregnancy tests may be conducted throughout the study in sufficient number, as determined by the Investigator or required by local regulations, to establish the absence of pregnancy during the study. The SV2 results must be available and must be negative before the subject takes the first dose of study drug. A FSH test will be performed at SV2 for post-menopausal females.
- **Complete Blood Count (CBC)**: A CBC with differential will be performed at Baseline/Day 1 and at Visit 14 (EOT). At all other noted visits in [Appendix A: Schedule of Activities](#), including SV1 and SV2, a CBC without differential will be performed. The CBC without differential will include: Hb, hematocrit, RBCs, mean corpuscular Hb, mean corpuscular Hb concentration, red cell width distribution, white blood cell count and platelets. The CBC with differential will include the same parameters as CBC without differential with the addition of white blood cell count with differential (neutrophils, lymphocytes, monocytes, eosinophils, basophils).

Hb will be monitored throughout the study via central laboratory to determine the dose of study drug (vadadustat or epoetin alfa) that subjects will receive. Refer to [Section 8.4.3, Measurement of Hb Levels for Dose Adjustment Consideration](#). Hb levels can be measured more frequently based on Investigator's clinical judgment.

- **Reticulocyte Count**: An automated reticulocyte count (both absolute and percent) will be performed at Baseline/Day 1 and at Visits 2, 4, 6, 8, 9, 10, 12, and 14 (EOT).

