### 11.1 Sample Size Estimation

Approximately 95 subjects are planned for enrollment in the Main study with 40 and 55 subjects randomized to the low epoetin alfa dose group and the high epoetin alfa dose group, respectively. Approximately 30 subjects are planned for enrollment in the ESA hyporesponder parallel study.

Sample size reflects the exploratory nature of this study.

Enrollment may be increased by up to 20 additional subjects in the Main study and by up to 30 additional subjects in the ESA hyporesponder parallel study to ensure adequate data is captured for the primary, PK/PD, and safety endpoints.

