### 13.2 Protocol Deviations

A protocol deviation is generally an unplanned excursion from the protocol that is not implemented or intended as a systematic change. The Investigator is responsible for ensuring the study is conducted in accordance with the procedures and evaluations described in this protocol and must protect the rights, safety, and welfare of subjects. The Investigator should not implement any deviation from, or changes of, the protocol, unless it is necessary to eliminate an immediate hazard to trial subjects.

A protocol waiver is a documented prospective approval of a request from an Investigator to deviate from the protocol. Protocol waivers are strictly prohibited.

For the purposes of this protocol, deviations requiring notification to Sponsor are defined as any subject who:

- Entered into the study even though they did not satisfy entry criteria.
- Developed withdrawal criteria during the study and not withdrawn.
- Received wrong treatment or incorrect dose.
- Received excluded concomitant treatment.

When a deviation from the protocol is identified for an individual subject, the Investigator or designee must ensure the Sponsor is notified. The Sponsor will follow-up with the Investigator, as applicable, to assess the deviation and the possible impact to the safety and/or efficacy of the subject to determine subject continuation in the study.

If a deviation impacts the safety of a subject, the investigator must contact the Sponsor immediately.

The Investigator will also assure that deviations meeting IRB/IEC and applicable regulatory authorities' criteria are documented and communicated appropriately. All documentation and communications to the IRB/IEC and applicable regulatory authorities will be provided to the Sponsor and maintained within the Trial Master File.

**Note:** Other deviations outside of the categories defined above that are required to be reported by the IRB/IEC in accordance with local requirements will be reported, as applicable.

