
	
19. For female subjects:
 

Of non-childbearing potential

Inability to confirm surgical sterility (e.g., hysterectomy, bilateral tubal ligation, bilateral oophorectomy) at least 1 month prior to Screening, or

Not considered post-menopausal (no menses for >1 year with follicle stimulating hormone >40 U/L at Screening)

Or, if of childbearing potential

Lack of confirmation of the use of acceptable forms of contraception* for a minimum of one complete menstrual cycle prior to Screening

Positive serum pregnancy test at SV2

Unwilling to use two acceptable forms of contraception* (at least one of which must be a barrier method) starting Baseline/Day 1, throughout the Treatment Period and for 30 days after the final study drug administration

 
20. Breastfeeding during Screening or throughout the Treatment Period and for 30 days after the final study drug administration.
 
21. Donation of ova starting at Screening, throughout the Treatment Period, and for 30 days after the final study drug administration.
 
22. Male subjects who have not had a vasectomy and do not agree to the following: use of an acceptable form of contraception* during the study and for 30 days after the last dose of the study drug; to not donate semen during the study and for at least 30 days after the last dose of vadadustat.
 
23. Subjects with bilateral native nephrectomy.
 
24. Any other reason, which in the opinion of the Investigator, would make the subject not suitable for participation in the study.

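### Exclusion 19 joins two negative conditions with *or*, so read literally it shuts out every woman of non-childbearing potential who is only surgically sterile or only post-menopausal, although Section 9.1.5 accepts either

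*Protocol*

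**What the plan says.** Section 7.3 opens with the rule that applies to the whole list: "Subjects must not meet any of the following exclusion criteria". Under criterion 19, the branch for women of non-childbearing potential has two items. The first reads "Inability to confirm surgical sterility (e.g., hysterectomy, bilateral tubal ligation, bilateral oophorectomy) at least 1 month prior to Screening, or". The second begins "Not considered post-menopausal (no menses for" and goes on to ask for more than one year without menses and an FSH above 40 U/L at Screening. The synopsis has the same two items with the same connector, and so do both protocol versions in the document.

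Section 9.1.5 defines the same group in positive terms. Its first route is "Confirmation of surgical sterility (e.g., hysterectomy, bilateral tubal ligation, bilateral oophorectomy) at least 1 month prior to Screening, or", and its second is "Post-menopausal (no menses for >1 year with FSH >40 U/L at Screening".

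Section 9.2.2 sets out who has the hormone measured: "A FSH test will be performed at SV2 for post-menopausal females". Section 9.3.1.2 and the Appendix A footnote on the pregnancy test say the same.

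Section 13.2 lists the deviations that must be notified to the sponsor. One is a subject who "Entered into the study even though they did not satisfy entry criteria".

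**The concern.** Section 9.1.5 accepts sterility or menopause. Turning that into an exclusion means negating the whole statement, and the negation of *S or M* is *not S and not M*. Criterion 19 negates each part but keeps *or*. Under a rule that any one criterion excludes, this changes who may enter.

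A post-menopausal woman who was never sterilised fails the first item. A pre-menopausal woman after hysterectomy fails the second. Section 9.1.5 accepts both. About 40 sites are planned, and each would have two written rules that give opposite answers for the same woman. What is at stake is consistent screening and a clean deviation record.

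**Working it through.** No sample size, power or error-rate figure is involved ("Sample size reflects the exploratory nature of this study"), so the check is one of logic.

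**Definitions.** S = surgical sterility confirmed as criterion 19 requires. M = post-menopausal by the menses and FSH definition, which is the same in Sections 7.3 and 9.1.5.

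**Rules.**
- Section 7.3, criterion 19: exclude if (not S) or (not M). Entry therefore needs S and M.
- Section 9.1.5: the woman qualifies if S or M.

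| S | M | Criterion 19 as written | Section 9.1.5 | Agree? |
|---|---|---|---|---|
| yes | yes | may enter | qualifies | yes |
| yes | no | excluded | qualifies | **no** |
| no | yes | excluded | qualifies | **no** |
| no | no | excluded | does not qualify | yes |

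The passages disagree in two of four rows. If the items were joined by *and* (exclude only if neither S nor M holds), all four rows would agree.

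**Is there a harmless reading?** One could try to read the first item's inability to confirm as covering both conditions, so that the woman is excluded only if neither can be confirmed. The text resists this. The second item carries its own negative and is a separate list entry, and in the childbearing branch of the same criterion each entry clearly excludes by itself.

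**Does the schedule support the literal rule?** No. FSH is scheduled only for women already regarded as post-menopausal. A sterile pre-menopausal woman has no scheduled test for the second item, so the procedures treat the two conditions as alternatives.

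**Can the effect be sized?** Among women who satisfy Section 9.1.5, the share excluded by the literal text is 1 − P(S and M) / P(S or M). The documents give neither P(S) nor P(M). The values below are assumptions that only show the spread, with S and M taken as independent:
- S = 30%, M = 70%: both 0.21, either 0.30 + 0.70 − 0.21 = 0.79, excluded 1 − 0.21/0.79 = 73%.
- S = 50%, M = 90%: both 0.45, either 0.95, excluded 1 − 0.45/0.95 = 53%.
- S = 80%, M = 80%: both 0.64, either 0.96, excluded 1 − 0.64/0.96 = 33%.

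Without independence, the result at S = M = 50% can lie anywhere from 0% (complete overlap) to 100% (no overlap). The share depends wholly on inputs that the documents do not supply.

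**The case against.** The strongest reply is that the intent is plain. Section 9.1.5 states the either/or definition, the FSH schedule fits it, and criterion 19 refers to Section 9.1.5, though only in its childbearing branch. Many sites would probably apply the intended rule. This stands as a reason to grade the point low. It does not make the written criterion correct.

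A second reply concerns versions. Sections 9.1.5, 9.2.2 and 13.2 can be read only in the earlier version, because the later version's text at hand stops at the start of Section 9. This also stands. The contradiction is verified within the earlier version. For the later one, what is verified is that criterion 19 keeps the same connector in Section 7.3 and the synopsis.

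A reader might also infer more than the documents support:
- *That most such women are excluded, or that a given number of subjects is lost.* No shares are given. Exclusions also act on screened women, while the enrolment target stays at about 125, so the effect would be extra screen failures and possibly a changed mix of subjects.
- *That women enrolled under Section 9.1.5 would leave the per-protocol population.* Section 11.2 removes subjects only for major deviations that bear on the primary endpoint analyses, to be specified before database lock. Sterility or menopausal status has no evident bearing on change in Hb.
- *That the ban on waivers in Section 13.2 blocks any solution.* A waiver there is advance permission to depart from the protocol. A sponsor's clarification of which of two conflicting passages governs is a different thing.

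**Conclusion.** The point holds as a contradiction in the eligibility wording. Read literally, criterion 19 excludes every woman of non-childbearing potential who meets exactly one of the two conditions, and Section 9.1.5 accepts all of them. This follows from the text alone and rests on no assumed figure.

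The consequence is either avoidable screen failures and uneven screening across sites, or enrolments that count as entry-criteria deviations to be notified. Its size cannot be given from the documents. No endpoint, randomisation, sample size or analysis population is shown to be affected. The point is minor, but it should be corrected because a stated rule, followed exactly, turns away subjects whom the protocol elsewhere accepts.

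**What to change.** Reconcile criterion 19 in Section 7.3 and in the synopsis with Section 9.1.5. Either reword the non-childbearing limb so that it excludes only a woman who is neither confirmed surgically sterile nor post-menopausal as Section 9.1.5 defines these, or replace the limb with a direct reference to that definition. The reference may be tidier. After the rewording the limb is largely redundant, since a woman who meets neither condition falls outside the non-childbearing group of Section 9.1.5 and belongs under the childbearing limb. Check that the later version's own Section 9.1.5 still carries the either/or definition.

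The change is one connector or one cross-reference in two places. It needs a protocol amendment with prospective IRB approval under Section 15.2, so it is not free, but it can travel with any other amendment. No analysis or data collection changes.
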